## 9.5.2 Safety Analysis Populations

Safety analyses will be conducted in the All Participants as Treated (APaT) population, which consists of all randomized participants who received at least one dose of study vaccination. Participants will be included in the group corresponding to the study vaccination they actually received for the analysis of safety data using the APaT population. This will be the group to which they are randomized except for participants who take incorrect study vaccination; such participants will be included in the vaccination group corresponding to the study vaccination actually received. Safety parameters for cross-treated participants (ie, those who received vaccinations of both V114 and Prevnar 13TM) will be summarized separately.

At least 1 temperature measurement obtained after study intervention is required for inclusion in the analysis of temperature.

#### 9.6 Statistical Methods

Statistical testing and inference for immunogenicity and safety analyses are described in Section 9.6.1 and Section 9.6.2, respectively. Unless otherwise stated, all statistical tests will be conducted at the  $\alpha$ =0.05 (2-sided) level. Section 9.6.3 describes how demographic and baseline characteristics will be summarized.

# 9.6.1 Statistical Methods for Immunogenicity

This section describes the statistical methods that address the primary, secondary, and exploratory immunogenicity objectives. The analyses will be conducted for each of the 15 pneumococcal serotypes in V114 and each antigen in the concomitant vaccines separately.

## Primary Endpoints/Hypotheses (H1 and H2)

The first primary objective is to compare the response rates of anti-PnPs serotype-specific IgG between V114 and Prevnar  $13^{TM}$  at 30 days PD3. The response rate is defined as the proportion of participants with anti-PnPs serotype-specific IgG responses achieving the threshold value of  $0.35~\mu g/mL$ . The objective will be assessed via the following non-inferiority hypotheses:

 $H_0$ :  $p_1$ - $p_2 \le -0.1$  versus  $H_1$ :  $p_1$ - $p_2 \ge -0.1$ .

V114-029-02 FINAL PROTOCOL

For the 13 shared serotypes contained in V114 and Prevnar 13TM, p1 is the response rate for the V114 group and p2 is the response rate for the Prevnar 13TM group. For the 2 serotypes unique to V114, p1 is the response rate of the 2 unique serotypes for the V114 group and p2 is the lowest response rate among all 13 shared serotypes, excluding serotype 3, for the Prevnar 13TM group. V114 is non-inferior to Prevnar 13TM if the lower bound of the 2-sided 95% CI for the between-treatment differences (V114 minus Prevnar 13TM) is greater than -0.1. The M&N method (1985), an unconditional, asymptotic method, will be used for this analysis [Miettinen, O. and Nurminen, M. 1985].

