## 4.2.1 Rationale for Endpoints

## 4.2.1.1 Immunogenicity Endpoints

The immunogenicity endpoints are consistent with previous studies evaluating PCVs (for the 13 shared serotypes between V114 and Prevnar 13TM) and the concomitantly administered pediatric vaccines in this study.

The 2 unique V114 serotypes will be evaluated for non-inferiority to the immune response of the lowest of any of the shared serotypes in Prevnar 13TM, excluding serotype 3, in alignment with the guidelines for the assessment of immune responses to PCVs from the World Health Organization [World Health Organization 2013]. For these comparisons, Prevnar 13TM serotype 3 immune responses will be excluded as the immunological profile of serotype 3 is not consistent with the performance of other Prevnar 13TM vaccine serotypes.

The pneumococcal electrochemiluminescence (PnECL) assay and the multiplexed opsonophagocytic assay (MOPA) will be used to measure vaccine-induced, anti-PnPs serotype-specific immune responses for all 15 serotypes included in V114. PnECL measures serotype-specific IgG GMCs (primary endpoint), and MOPA measures serotype-specific OPA GMTs (secondary endpoint). OPA GMTs represent functional antibodies capable of inhibiting growth of *S. pneumoniae* in culture. Additional information on the immunogenicity assays can be found in Section 8.2.

MOPA requires a large volume of serum, which is difficult to obtain from infants. The PnECL assay requires less serum, and several studies have shown a positive correlation between serotype-specific IgG antibody concentrations and OPA titers in children and adults [Centers for Disease Control and Prevention 2010] [Anttila, M., et al 1999] [Romero-Steiner, S., et al 1997]. For these reasons, the PnECL will be used to test the primary immunogenicity hypotheses in this study.

The use of the serotype-specific IgG antibody level of  $\geq 0.35~\mu g/mL$  has been recommended by a World Health Organization (WHO) expert panel as an acceptable threshold value for evaluating the clinical performance of PCVs following a routine childhood vaccination regimen [World Health Organization 2008] [World Health Organization 2005]. The response rate (ie, the proportion of participants meeting the serotype-specific IgG threshold value of  $\geq 0.35~\mu g/mL$ ) is a primary endpoint in this study.

Anti-PnPs serotype-specific IgG and OPA responses will be measured at 3 time points:

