## 9 STATISTICAL ANALYSIS PLAN

This section outlines the statistical analysis strategy and procedures for the study. If, after the study has begun, but prior to any unblinding, changes are made to primary and/or key secondary hypotheses, or the statistical methods related to those hypotheses, then the protocol will be amended (consistent with ICH Guideline E-9). Changes to exploratory or other non-confirmatory analyses made after the protocol has been finalized, but prior to unblinding, will be documented in a supplemental Statistical Analysis Plan and referenced in the Clinical Study Report (CSR) for the study. Post hoc exploratory analyses will be clearly identified in the CSR.

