# Primary Endpoints/Hypotheses (H3 to H6)

The second primary objective and the third primary objective are to compare the anti-PnPs serotype-specific IgG GMCs between V114 and Prevnar 13TM at 30 days PD3 and 30 days PD4, respectively. The objectives will be assessed via the following non-inferiority hypotheses:

 $H_0$ :  $GMC_1/GMC_2 \le 0.5$  versus  $H_1$ :  $GMC_1/GMC_2 > 0.5$ .

For the 13 shared serotypes contained in V114 and Prevnar 13TM, GMC1 is the anti-PnPs serotype-specific IgG GMCs for the V114 group and GMC2 is the anti-PnPs serotype-specific IgG GMCs for the Prevnar 13TM group. For the 2 serotypes unique to V114, GMC1 is the anti-PnPs serotype-specific IgG GMCs of the 2 unique serotypes for the V114 group and GMC2 is the lowest anti-PnPs IgG GMCs among all 13 shared serotypes, excluding serotype 3, for the Prevnar 13TM group. A ratio of 0.5 corresponds to a 2.0-fold decrease of anti-PnPs serotype-specific IgG GMCs in the V114 group as compared with the Prevnar 13TM group. V114 is non-inferior to Prevnar 13TM if the lower bound of the 2-sided 95% CI for the GMC ratios (V114/Prevnar 13TM) is greater than 0.5. Estimation of the IgG GMC ratios and computation of the corresponding 95% CIs will be calculated using t-distribution with the variance estimate from a linear model utilizing the log-transformed antibody concentrations as the response and a single term for vaccination group.

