## 9.8 Multiplicity

The study will be considered to have met its primary objectives if non-inferiority is demonstrated for the 13 shared serotypes and for the 2 unique serotypes for IgG GMCs and IgG response rates at 30 days PD3 and for IgG GMCs at 30 days PD4. All hypotheses will be tested individually for each serotype at a 1-sided 0.025 alpha level. This approach controls the 1-sided type-I error rate at 0.025, thus no multiplicity adjustment is required.

93

The study will be considered to have met its secondary objective for a specific concomitant vaccine if non-inferiority is demonstrated for all the antigens included in that concomitant vaccine. The study will be considered to have met its secondary objective for the superiority hypotheses for the 2 unique V114 serotypes if superiority is demonstrated for the 2 unique serotypes for IgG GMCs and IgG response rates at 30 days PD3 and for IgG GMCs at 30 days PD4. The study will be considered to have met its secondary objective for the superiority hypotheses for serotype 3 if superiority is demonstrated for IgG response rates and IgG GMCs at 30 days PD3 and IgG GMCs at 30 days PD4.

No multiplicity adjustments will be made for the safety comparisons.

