## Primary Immunogenicity Endpoints/Hypotheses (H1 and H2)

This study has >95% power at a 1-sided 2.5% alpha-level to demonstrate V114 is non-inferior to Prevnar 13TM for the 13 shared serotypes and the 2 unique serotypes based on the proportion of participants with anti-PnP serotype-specific IgG responses achieving the threshold value of 0.35 μg/mL at 30 days PD3. This power is calculated based on (1) 80% evaluability rate (688 evaluable participants per treatment group), (2) a non-inferiority margin of -0.1 for the difference (V114 minus Prevnar 13TM), and (3) a serotype-specific true response rate for the 13 shared serotypes between V114 and Prevnar 13TM and the 2 unique V114 serotypes (Table 8).

16-MAR-2021

PROTOCOL/AMENDMENT NO.: 029-02

Table 8 Assumptions of the True Response Rates for V114 and Prevnar 13TM for the 15 Pneumococcal Serotypes in V114 at 30 Days PD3

S	True Re	sponse Rate
Serotype	V114	Prevnar 13 TM
Prevnar 13 TM Types	•	·
1	0.95	0.95
3	0.90	0.70
4	0.95	0.95
5	0.95	0.95
6A	0.95	0.95
6B	0.90	0.90
7F	0.95	0.95
9V	0.95	0.95
14	0.95	0.95
18C	0.95	0.95
19A	0.95	0.95
19F	0.95	0.95
23F	0.90	0.90
Non- Prevnar 13 TM Types		
22F	0.95	NA
33F	0.90	NA

NA=not applicable; PD=postdose.

Comparison for the 2 unique V114 serotypes will be to the lowest responder among the shared serotypes in Prevnar 13TM, excluding serotype 3. Based on our assumption, the comparator could be either serotype 6B or 23F (true response rate=0.90).

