## Primary Immunogenicity Endpoints/Hypotheses (H3 and H4)

This study has >95% power at a 1-sided 2.5% alpha-level to demonstrate V114 is non-inferior to Prevnar 13TM for the 13 shared serotypes and the 2 unique serotypes based on the anti-PnP serotype-specific IgG GMCs at 30 days PD3. This power is calculated based on (1) 80% evaluability rate (688 evaluable participants per treatment group), (2) a non-inferiority margin of 0.5 for the GMC ratio (V114/Prevnar 13TM), (3) a true GMC ratio of 1.0 for the 13 shared serotypes between V114 and Prevnar 13TM and for the 2 unique serotypes between V114 and the lowest GMC of any of the shared serotypes in Prevnar 13TM, excluding serotype 3, and (4) the standard deviation of the natural log concentrations is 1.1 for the 13 shared serotypes between V114 and Prevnar 13TM and the 2 unique serotypes in V114.

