#### Primary Endpoints/Hypotheses (H1 and H2)

The first primary objective is to compare the response rates of anti-PnPs serotype-specific IgG between V114 and Prevnar 13TM at 30 days PD3. The response rate is defined as the proportion

of participants with anti-PnPs serotype-specific IgG responses achieving the threshold value of  $0.35 \mu g/mL$ . The objective will be assessed via the following non-inferiority hypotheses:

$$H_0$$
:  $p_1$ - $p_2 \le -0.1$  versus  $H_1$ :  $p_1$ - $p_2 \ge -0.1$ .

For the 13 shared serotypes contained in V114 and Prevnar 13TM, p1 is the response rate for the V114 group and p2 is the response rate for the Prevnar 13TM group. For the 2 serotypes unique to V114, p1 is the response rate of the 2 unique serotypes for the V114 group and p2 is the lowest response rate among all 13 shared serotypes, excluding serotype 3, for the Prevnar 13TM group. V114 is non-inferior to Prevnar 13TM if the lower bound of the 2-sided 95% CI for the between-treatment differences (V114 minus Prevnar 13TM) is greater than -0.1. The M&N method (1985), an unconditional, asymptotic method, will be used for this analysis [Ref. 5.4: 03QCDT].

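### H2 tests 22F and 33F against whichever Prevnar 13 serotype is observed lowest, so the unqualified 0.025 type I error statement in protocol 9.8 and sSAP 3.8 does not hold in general

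*Combined protocol and SAP*

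**What the plan says.** Protocol 9.6.1 (H1 and H2) defines p2, the comparator rate for the two unique serotypes, as the rate that "is the lowest response rate among all 13 shared serotypes, excluding serotype 3, for the Prevnar" 13 group. sSAP 3.6.1 uses the same rule ("lowest response rate among all 13 shared serotypes, excluding serotype 3, for the Prevnar" 13 group). Thirteen shared serotypes less serotype 3 leaves 12 candidates. Non-inferiority requires the lower limit of an ordinary two-sided 95% M&N interval to exceed -0.1.

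The note to protocol Table 8 (sSAP Table 6) does not fix the comparator. It says that "the comparator could be either serotype 6B or 23F (true response rate=0.90"). The other ten candidates are assumed to be at 0.95.

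Protocol 9.8 and sSAP 3.8 require every serotype to pass, each at one-sided 0.025, and conclude: "This approach controls the 1-sided type-I error rate at 0.025, thus no multiplicity adjustment is required".

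The lowest-serotype rule is deliberate. Protocol 4.2.1.1 describes it as "in alignment with the guidelines for the assessment of immune responses to PCVs". The GMC comparisons H4 and H6 follow the same pattern: the reference value "is the lowest anti-PnPs IgG GMCs among all 13 shared serotypes, excluding serotype 3".

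**The concern.** An all-must-pass rule controls error at 0.025 only if each component test has level 0.025. The H2 component uses a comparator chosen by looking at the results. If two Prevnar 13 serotypes have equal or nearly equal true rates, the lower of the two observed rates tends to fall below the true value. The V114 serotype is then compared with a target that is slightly too low, and the M&N bound treats that target as if it had been named in advance.

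H2 is a primary hypothesis and concerns the two serotypes that distinguish V114 from the comparator. What is at stake is whether the stated error rate of that test is correct, and by how much it is off.

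**Working it through.** **Inputs from the documents.** 860 randomized per arm and 80% evaluability, so 0.80 × 860 = 688 per arm. Margin -0.1, one-sided 0.025, M&N method. Prevnar 13 rates: 6B and 23F at 0.90, the other ten candidates at 0.95. V114 rates: 33F at 0.90, 22F at 0.95.

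**Added assumptions.** (a) Table 8 gives power assumptions, so an error rate needs a null value: 0.90 - 0.10 = 0.80 for one unique serotype. (b) The documents give no within-infant correlation between serotypes, so a range is shown. (c) The lowest rate is read as the lowest observed rate. With no serotype named, this is the only workable reading.

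**Step 1: the plan's power figure.** At 0.90 against 0.90, the SE is √(2 × 0.90 × 0.10/688) = 0.0162. Then 0.10/0.0162 - 1.96 = 4.2, which gives power above 99.99%. All 15 serotypes together, if independent, also exceed 99.99%. The stated power of more than 95% reproduces.

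**Step 2: a comparator fixed in advance.** The test passes when

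z = (x1/n - x2/n + 0.1) / √{[p̃1(1 - p̃1)/n + p̃2(1 - p̃2)/n] × 2n/(2n - 1)} > 1.96,

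where p̃1 and p̃2 are the maximum-likelihood estimates restricted to p̃1 = p̃2 - 0.1. Exact enumeration with X1 ~ Bin(688, 0.80) and X2 ~ Bin(688, 0.90) gives 0.0246, which agrees with the nominal 0.025.

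**Step 3: the lower of two tied serotypes, independent.** Let Y = min(X2, X3), so that P(Y ≥ y) = P(X2 ≥ y)². The error is the sum over y of P(Y = y) × P(X1 ≥ c(y)), where c(y) is the smallest passing count.
- The mean observed minimum is 0.8936, about 0.6 points below 0.90.
- The error is **0.0420**. Adding the ten candidates at 0.95 leaves it at 0.0420.
- Normal check: passing against the minimum means that at least one of two z statistics exceeds 1.96. Their correlation is 0.16/(0.16 + 0.09) = 0.64, which gives 0.0430.

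**Step 4: within-infant correlation (latent normal), tie at 0.90.**

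| Latent correlation | 0 | 0.5 | 0.8 | 0.95 | 1 |
|---|---|---|---|---|---|
| Error | 0.042 | 0.040 | 0.037 | 0.034 | 0.0246 |

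Latent 0.5, 0.8 and 0.95 correspond to correlations of 0.25, 0.51 and 0.76 between the yes/no responses.

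**Step 5: other configurations.**

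| Configuration | Error |
|---|---|
| Lowest two differ by 0.5 points (latent correlation 0.95 to 0) | 0.027 to 0.033 |
| Differ by 1 point | 0.025 to 0.028 |
| Differ by 2 points | 0.025 |
| Two-way tie at 0.85, independent | 0.0437 |
| Two-way tie at 0.80, independent | 0.0443 |
| Three-way tie at 0.90, independent | 0.0558 |

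**Step 6: does the all-must-pass rule remove it?** No. With 33F at 0.80 and 22F at 0.95, both pass H2 with probability 0.0420. If both sit at the margin and are independent, the probability is 0.005, so the figure applies when one is at the margin and the other clearly passes.

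H4 gives little protection for 33F. The plan states that "the standard deviation of the natural log concentrations is 1.1 for the 13 shared serotypes", and uses the same SD for the two unique ones. With log-normal data (an added assumption) and the 0.35 threshold, 0.80 corresponds to a GMC of 0.883 and 0.90 to 1.433. The ratio is 0.616, above the 0.5 limit. In simulation the joint H2 and H4 pass rate was 0.0415 at correlation 0 and 0.0333 at 0.95, essentially that of H2 alone.

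**Step 7: size on the margin scale.** Under the 0.90 tie, the pass rate falls back to 0.0246 at a true unique-serotype rate of 0.7956 (correlation 0) to 0.7974 (0.95). That is a margin of 10.26 to 10.44 points. At a true 11-point deficit the false pass rate is 0.9% to 1.2%, against 0.65% with a fixed comparator.

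**The case against.** The strongest reply has four parts. The sentence in 9.8 explains why testing many serotypes under an all-must-pass rule needs no split of alpha, and that logic is correct. The selection is disclosed: the rule, its guideline basis and the open choice between 6B and 23F are all in the protocol. The 0.042 needs several things at once: an exact tie, independent responses within the same infant, and one unique serotype exactly at the margin. The equal entries in Table 8 are round planning values and do not show that the true rates tie. Finally, no decision changes.

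Most of this stands, and it is why the point is minor. It does not make the sentence true. The all-must-pass argument takes the level of each component as given, and the H2 component does not have that level at the tie the plan itself assumes. Correlation reduces the excess but removes it only as it approaches 1.

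A reader might infer more than the documents support:
- That 0.042 is a ceiling. It is not, as the ties at lower rates and the three-way tie show.
- That 12 candidates mean a twelve-way selection. Twelve independent serotypes all tied at 0.90 would give 0.125, but the plan puts ten of them at 0.95, where they add nothing.
- That the lowest-serotype rule is itself a flaw. It is guideline-aligned and is not in question.
- That H4 and H6 carry the same error. They use the same rule, but the documents state no GMC tie, so no figure is claimed for them.

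**Conclusion.** The concern holds as a correction to a stated property of a primary test. Protocol 9.8 and sSAP 3.8 say that one-sided error is controlled at 0.025. For H2 that is a nominal level. It is accurate when one eligible Prevnar 13 serotype is lowest by about 2 points. At the two-way tie at 0.90 it becomes about 0.042 with independent responses, or about 0.034 to 0.040 at latent correlation 0.95 to 0.5. More ties or lower tied rates give more.

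These figures rest on 688 evaluable per arm, the added null value of 0.80 for one unique serotype, the other clearly passing, and the assumed correlations. They are error rates for H2 (with H4 checked for 33F only), not for overall primary success, which also requires H6 at PD4; no joint rate with H6 was calculated. The power statement is unaffected. The effect, about 0.3 to 0.4 points of margin, is minor.

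**What to change.** Keep the comparator rule, the margin, the sample size and the success rule. Amend the sentence in protocol 9.8 and sSAP 3.8 to say, in substance:

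> For H2, H4 and H6 the comparator serotype is selected from the data, so 0.025 is a nominal one-sided level. For H2 it holds when one Prevnar 13 serotype is clearly lowest (by about 2 percentage points). Under a two-way tie at 0.90 with 688 evaluable participants per group, the H2 error is about 0.034 to 0.042 for assumed latent within-infant correlation from 0.95 to 0. It is higher with more tied serotypes or lower tied rates.

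The cost is one short paragraph in each document. Section 9.8 is protocol text, so correcting it takes a protocol amendment as well as an sSAP revision. The rule at the start of protocol section 9 covers changes to the primary or key secondary hypotheses "or the statistical methods related to those hypotheses, then the protocol will be amended". This edit changes neither a hypothesis nor a method; the amendment is needed only because of where the sentence stands. No additional interval or test is needed.

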# Primary Endpoints/Hypotheses (H3 to H6)

The second primary objective and the third primary objective are to compare the anti-PnPs serotype-specific IgG GMCs between V114 and Prevnar 13TM at 30 days PD3 and 30 days PD4, respectively. The objectives will be assessed via the following non-inferiority hypotheses:

 $H_0$ :  $GMC_1/GMC_2 \le 0.5$  versus  $H_1$ :  $GMC_1/GMC_2 > 0.5$ .

For the 13 shared serotypes contained in V114 and Prevnar 13TM, GMC1 is the anti-PnPs serotype-specific IgG GMCs for the V114 group and GMC2 is the anti-PnPs serotype-specific IgG GMCs for the Prevnar 13TM group. For the 2 serotypes unique to V114, GMC1 is the anti-PnPs serotype-specific IgG GMCs of the 2 unique serotypes for the V114 group and GMC2 is the lowest anti-PnPs IgG GMCs among all 13 shared serotypes, excluding serotype 3, for the Prevnar 13TM group. A ratio of 0.5 corresponds to a 2.0-fold decrease of anti-PnPs serotype-specific IgG GMCs in the V114 group as compared with the Prevnar 13TM group. V114 is non-inferior to Prevnar 13TM if the lower bound of the 2-sided 95% CI for the GMC ratios (V114/Prevnar 13TM) is greater than 0.5. Estimation of the IgG GMC ratios and computation of the corresponding 95% CIs will be calculated using t-distribution with the variance estimate from a linear model utilizing the log-transformed antibody concentrations as the response and a single term for vaccination group.

# **Secondary Endpoints/Hypotheses (H7 to H11)**

To address the secondary objectives for evaluating the concomitant vaccines, between-group comparison will be made based on the response rate of the antigens contained in PentacelTM at 30 days PD3 and the antigens contained in VAQTATM, M-M-RTMII, VARIVAXTM, and HIBERIXTM at 30 days PD4. The response rate is defined as the proportion of participants achieving the antigen-specific threshold value (Table 5 in Section 9.4.1). Each objective will be assessed via the following non-inferiority hypotheses:

H0:  $p_1-p_2 \le \delta$  versus H1:  $p_1-p_2 > \delta$ ,

where  $p_1$  is the response rate for the V114 group,  $p_2$  is the response rate for the Prevnar  $13^{TM}$  group, and  $\delta$  is the pre-specified non-inferiority margin and the values of  $\delta$  are listed in Table 9 in Section 9.9. The concomitant vaccine administered concomitantly with V114 is non-inferior to the concomitant vaccine administered concomitantly with Prevnar  $13^{TM}$  if the lower bound of the 2-sided 95% CI for the between-treatment differences (V114 minus Prevnar  $13^{TM}$ ) is greater than  $\delta$ . The M&N method (1985) will be used for this analysis.

In addition, the between-group comparison will be made based on the antigen-specific GMCs of pertussis contained in PentacelTM at 30 days PD3. The objective will be assessed via the following non-inferiority hypotheses:

 $H_0$ :  $GMC_1/GMC_2 \le 0.67$  versus

 $H_1: GMC_1/GMC_2 > 0.67$ ,

V114-029-02 FINAL PROTOCOL

16-MAR-2021

PROTOCOL/AMENDMENT NO.: 029-02

where GMC1 is the antigen-specific pertussis GMCs for the V114 group and GMC2 is the antigen-specific pertussis GMCs for the Prevnar 13TM group. A ratio of 0.67 corresponds to a 1.5-fold decrease of antigen-specific pertussis GMCs in the V114 group as compared with the Prevnar 13TM group. V114 is non-inferior to Prevnar 13TM if the lower bound of the 2-sided 95% CI for the GMC ratios (V114/Prevnar 13TM) is greater than 0.67. Estimation of the GMC ratios and computation of the corresponding 95% CIs will be calculated using t-distribution with the variance estimate from a linear model utilizing the log-transformed antibody concentrations as the response and a single term for vaccination group.

